### **4.3 Evaluations At The Time Of Treatment Discontinuation**

At the time of treatment discontinuation all evaluations should be completed as soon as possible (see Appendix I, Schedule of Events). The following should be performed upon discontinuation of study drug:

- 4.3.1 Complete blood count with differential and platelets.
- 4.3.2 Serum chemistries: liver enzymes (SGOT, SGPT, alkaline phosphatase), BUN, creatinine, electrolytes, bilirubin (direct and indirect) and phosphate.
  - 4.3.2.1 Urine phosphate and creatinine for calculation of fractional excretion of phosphate ( $FE_{PO_4}$ ). [Fractional excretion of phosphate = (spot urinary phosphate/serum phosphate)/(spot urinary creatinine/serum creatinine) × 100].
- 4.3.3 CD4 count and HIV plasma RNA viral load.
- 4.3.4 HHV-8 Viral Load (see Appendix XIII).
- 4.3.5 A complete physical exam including: vitals signs, weight, tumor assessment, Karnofsky performance status (Appendix IV), and toxicity evaluation. At the time of discontinuation, a lesion that is clearly growing or has not responded will be biopsied for receptor mutations. If possible, the lesion should be greater or equal to 5 x 5 mm. Biopsy should be performed with a 4 mm punch biopsy.

#### **4.4 Final Evaluations/Off Drug, Off Study**

AEs must be reported if the AE began any time within 8 weeks of receiving the study treatment. Additionally, if a site learns of any incidence of death, cancer or fetal anomaly, WHICH IS DRUG RELATED, at any time after the study is closed, the site should notify Novartis. This information may provide additional insight into the safety of Gleevec.

## 5.0 **STUDY TREATMENT**

### 5.1 **Drug Regimens, Administration And Duration**

Novartis will supply Gleevec as 100 mg tablets packaged in bottles. Medication labels will comply with the legal requirements of the U.S. and will be printed in English. The storage conditions for Gleevec will be described on the medication label. Bottles must be stored in a safe, secure location.

Gleevec is a local irritant and must be taken in a sitting position with a large (250 mL) glass of water. Direction of use on medication label: Take as directed with a large glass of water.

### 5.2 **Drug Orders, Transfers, Returns, And Accountability**

Gleevec will be provided by Novartis for the 12-month study period.

Questions about drug orders, transfers, returns, or accountability should be addressed to BIDMC IND Pharmacy, [name] at [contact], Monday through Friday between 9:00 am and 4:30 pm Eastern Time.

#### 5.2.1 Drug Orders

Once a patient has been registered with the AMC Operations Center, the enrolling site will fax a clinical drug request for that patient to the Beth Israel Deaconess Medical Center IND pharmacy. If the order is received prior to 1:00 pm Eastern Time, it will be processed by IND pharmacy and shipped that day; otherwise, drug orders will be shipped the following business day. The shipments will be sent via FedEx for next business day delivery. Thus, if a patient is registered on Wednesday, the order will be processed on Thursday and shipped on Friday for delivery on Monday. The initial request will be for a 4-week supply of Gleevec. Sites will be sent enough drug for 30 days to cover shipping time if the patient continues on the trial. Sites may reorder additional Gleevec by completing an NCI Clinical Drug Request form and faxing it to the BIDMC IND pharmacy at [contact]. The NCI Clinical Drug Request form is available on the NCI home page (<http://ctep.info.nih.gov>) or by calling the PMB at [contact]. The patient ID number (e.g. "042-999-999") and the patient initials (e.g., "LFM") should be entered in the *Patient or Special Code* field. All drug orders will be shipped to the pharmacy of the institution where the patient is enrolled.

#### 5.2.2 Drug Transfers

Drug may not be transferred from one patient to another patient, from one center to another center, or from one protocol to another protocol.

### 5.2.3 Drug Returns

All unused drug supplies should be destroyed on site and the amount recorded.

### 5.2.4 Drug Accountability

The Investigator, or a responsible party designated by the Investigator, must maintain a careful record of the receipt and disposition of all drugs received using the NCI Investigational Agent Accountability Record available on the CTEP home page (<http://nci.cancer.gov>) or by calling the PMB at [contact].

## 5.3 **Dosing**

Patients will be instructed to take Gleevec 400 mg/day (a total of 4 tablets). Patients who have been on study for at least 3 months without any toxicities may have their dose increased to 600 mg/day.

## 5.4 **Dose Modifications For Non-Hematological Toxicity**

Further continuation of Gleevec treatment after any interruptions lasting longer than 2 weeks is not recommended.

### 5.4.1 Grade 2

If the patient experiences a new Grade 2 non-hematologic toxicity, with the exception of hypophosphatemia, study drug must be withheld until the toxicity has resolved to  $\leq$  Grade 1. Gleevec may then be resumed at the same daily dose. If the Grade 2 toxicity recurs, Gleevec must be withheld until the toxicity has resolved to  $\leq$  Grade 1, and the daily dose must be reduced by 100 mg if at 400 mg dose level, or by 200 mg if at 600 mg dose level. If the Grade 2 toxicity recurs, Gleevec treatment will be stopped.

For Grade 2 hypophosphatemia the patient should be started on Neutra-Phos 250 mg by mouth four times a day.

Additionally, if a patient has a 25-hydroxy D that is  $> 30$  ng/mL, no Vitamin D supplementation is needed. If less than 20 ng/mL, give Ergocalciferol D2: 50,000 IU weekly x 8 weeks and then maintain with daily OTC Vitamin D3 cholecalciferol 1,000 IU daily. If the level is between 20 ng/mL and 30 ng/mL, calculate the additional Vitamin D the patient will need to add to their current intake by the formula:  $30 - (\text{current level}) \times 100 = \# \text{ IUs of OTC cholecalciferol to boost up stores to optimum level of } 30\text{ng/mL}$  (to increase by 1 ng/mL add 100 IU of Vitamin D3). For example if current level = 25 ng/mL, the patient will need to add 500 IU to their current intake. With

completely optimum Vitamin D levels, patients may be less susceptible to hypophosphatemia.

If the Grade 2 hypophosphatemia recurs in spite of supplementation, Gleevec must be withheld until the toxicity has resolved to  $\leq$  Grade 1, and the daily dose must be reduced by 100 mg if at 400 mg dose level, or by 200 mg if at 600 mg dose level. If the Grade 2 hypophosphatemia recurs after dose reduction, Gleevec treatment will be stopped.

#### 5.4.2 Grade 3/4

If the patient experiences Grade 3/4 toxicity, with the exception of hypophosphatemia, Gleevec must be withheld until the toxicity has resolved to  $\leq$  Grade 1 or baseline, and the daily dose must be reduced by 100 mg if at 400 mg dose level, or by 200 mg if at 600 mg dose level. If the Grade 3/4 toxicity recurs, Gleevec treatment will be stopped.

For Grade 3/4 hypophosphatemia the patient should be started on Neutra-Phos 250mg by mouth four times a day and Gleevec should be held until resolved to Grade  $\leq$  1 and then restarted at previous dose.

Additionally, if a patient has a 25-hydroxy D that is  $> 30$  ng/mL, no Vitamin D supplementation is needed. If less than 20 ng/mL, give Ergocalciferol D2: 50,000 IU weekly x 8 weeks and then maintain with daily OTC Vitamin D3 cholecalciferol 1,000 IU daily. If the level is between 20ng/mL and 30ng/mL, calculate the additional Vitamin D the patient will need to add to their current intake by the formula:

$30 - (\text{current level}) \times 100 = \# \text{ IUs of OTC cholecalciferol to boost up stores to optimum level of } 30\text{ng/mL}$  (to increase by 1 ng/mL, add 100 IU of Vitamin D3). For example if current level = 25ng/mL, the patient will need to add 500 IU to their current intake. With completely optimum Vitamin D levels, patients may be less susceptible to hypophosphatemia.

If Grade 3/4 hypophosphatemia recurs in spite of dose reduction, Gleevec must be withheld until the toxicity has resolved to  $\leq$  Grade 1 or baseline, and the daily dose must be reduced by 100 mg if at 400 mg dose level, or by 200 mg if at 600 mg dose level. If the Grade 3/4 hypophosphatemia recurs after dose reduction, Gleevec treatment will be stopped.

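### Section 5.4.2: the recurrence rule for Grade 3/4 hypophosphatemia presupposes a dose reduction that the first-episode rule never makes

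*Combined protocol and SAP*

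**What the plan says.** Section 5.4.2 takes hypophosphatemia out of the general Grade 3/4 rule, which opens "If the patient experiences Grade 3/4 toxicity, with the exception of hypophosphatemia". The summary table that follows 5.4.2 excludes it too, by its title. Grade 3/4 hypophosphatemia therefore has its own sequence in 5.4.2:

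- **First episode.** Start Neutra-Phos and hold imatinib to Grade 1 or lower; the drug is "and then restarted at previous dose".
- **Recurrence.** "If Grade 3/4 hypophosphatemia recurs in spite of dose reduction, Gleevec must be withheld until the toxicity has resolved to" Grade 1 or baseline, after which the daily dose is cut by 100 mg from 400 mg, "or by 200 mg if at 600 mg dose level".
- **Further recurrence.** "If the Grade 3/4 hypophosphatemia recurs after dose reduction, Gleevec treatment will be stopped".

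Section 5.4.1 sets out the Grade 2 sequence. At the first episode, "For Grade 2 hypophosphatemia the patient should be started on Neutra-Phos 250 mg by mouth four times a day", with no hold. At recurrence, "If the Grade 2 hypophosphatemia recurs in spite of supplementation, Gleevec must be withheld until the toxicity has resolved to" Grade 1 or lower, with the same 100 mg or 200 mg cut. A recurrence after that cut stops treatment.

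Section 5.3 starts every patient at 400 mg/day. An increase to 600 mg/day is allowed after at least 3 months on study free of toxicity.

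**The concern.** The recurrence sentence in 5.4.2 is the step that introduces a dose reduction for Grade 3/4 hypophosphatemia, yet its trigger requires that a reduction has already failed. A patient who was restarted at the same dose, as the first-episode rule directs, does not meet that trigger when the event returns. Nor does that patient meet the stop rule, which also requires an earlier reduction.

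This is an operative dosing instruction for a toxicity that section 1.1.3.5 names as a risk of imatinib, in a trial open to all sites of the consortium. A site applying the words as written could put a patient with recurrent Grade 3/4 hypophosphatemia back on the full dose, while a recurrent Grade 2 event under 5.4.1 requires a cut. The milder event would then be handled more strictly than the severe one, and sites could differ in what they do.

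**Working it through.** The plan states no figure to reproduce. The check is to follow each rule through successive episodes and see which instruction applies.

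| Episode | Grade 2 (5.4.1) | Grade 3/4 (5.4.2), as written | Grade 3/4, trigger changed to supplementation |
|---|---|---|---|
| First | Supplement, no hold | Supplement, hold, restart at same dose | Same as written |
| Recurrence at unreduced dose | Hold, then 400→300 or 600→400 mg | Neither reduce nor stop is triggered; at best the first-episode rule repeats | Hold, then 400→300 or 600→400 mg |
| Recurrence after that cut | Stop | Stop | Stop |

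**Does other text fill the empty cell?** No. The general Grade 3/4 rule and the summary table both exclude hypophosphatemia.

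**Is it a slip or a choice?** Three observations point to a slip.

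1. The 5.4.1 sentence has the same structure and the same dose steps, but its trigger is failure of supplementation. Putting that trigger into 5.4.2 gives a coherent order: same dose, reduce, stop.
2. The disputed sentence has a branch for patients at 600 mg. The protocol's dose levels are 300, 400 and 600 mg. Its listed reductions are 400 − 100 = 300 mg and 600 − 200 = 400 mg. None ends at 600 mg, which is reached only by escalation from 400 mg (5.3), and no re-escalation after a reduction is described. A patient at 600 mg therefore cannot have been reduced, so this branch contradicts the sentence's own trigger.
3. At the first episode the Grade 3/4 rule is stricter than the Grade 2 rule (hold plus phosphate, against phosphate alone). Only at recurrence does it become weaker, which is implausible as an intention.

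**Size of the dosing difference.**

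- At 400 mg: the missed cut is 100/400 = 25%; literal over intended restart dose is 400/300 = 1.33.
- At 600 mg: the missed cut is 200/600 = 33%; literal over intended restart dose is 600/400 = 1.50.

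The 400 mg case is the main one. All patients (30 at most, per the Schema) start there, and 600 mg is open only to those who qualify under 5.3.

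**The case against.** The strongest reply is that the rule can be recovered from its own text. The action names 400 and 600 mg, the 600 mg branch can only mean an unreduced patient, and the next sentence orders a stop after reduction. Read together, these give hold, reduce, stop. A site that compared 5.4.1 would probably reach the same reading. This stands, and it makes repeated restarts at full dose unlikely. It does not remove the need for a correction, because a site should not have to infer a safety rule by comparing two sections.

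A second reply is that the slip could lie elsewhere. The instruction to restart at the previous dose might be the error, since the general Grade 3/4 rule reduces at the first event. This is possible but weaker. The recurrence sentence would then order a second cut while the following sentence orders a stop, and section 1.1.3.5 reports that these abnormalities were managed without lowering the dose. The documents favour the supplementation reading without settling it.

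Third, the trigger is not wholly empty. A patient cut from 600 to 400 mg under another rule could literally meet it and go to 300 mg. For that patient the stop sentence could also be read to apply, an overlap that mostly disappears if the two sentences are taken in order. At 300 mg there is no overlap, because the reduce sentence specifies no cut from that level.

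Finally, the harm is limited. Each episode brings a hold and phosphate replacement. Section 4.2.1.5 includes phosphate in the chemistries at scheduled visits. Section 5.4 adds that "Further continuation of Gleevec treatment after any interruptions lasting longer than 2 weeks is not recommended". Section 7.0 lets the investigator withdraw a patient for reasons believed to be life-threatening. All of this is correct, but none of it supplies the missing reduction step.

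**Conclusion.** The concern holds. As written, 5.4.2 provides no route from a recurrence of Grade 3/4 hypophosphatemia at an unreduced dose to a dose reduction. That a wording error exists is clear from the text. The exact intended wording is an inference from 5.4.1 and from the 600 mg branch.

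Its importance is minor. The ratios of 1.33 and 1.50 describe the dosing difference if a site follows the literal text; they do not measure harm. The frequency of recurrent Grade 3/4 hypophosphatemia cannot be derived from the protocol, and section 1.1.3.5 suggests that a need for reduction may be uncommon. The primary response test, its power and the sample size are not affected.

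**What to change.** In the recurrence sentence of 5.4.2, replace *dose reduction* with *supplementation*, so that the trigger matches 5.4.1. The sequence then reads:

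1. First episode: supplement, hold to Grade 1 or lower, restart at the same dose.
2. Recurrence: hold, then reduce from 400 to 300 mg or from 600 to 400 mg.
3. Recurrence after that reduction: stop.

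The sponsor should confirm that this is the intended sequence before the text is amended. The cost is one phrase in one section, with no change to data collection, analysis or sample size.

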## Summary of Dose Modifications for Non-Hematologic Toxicity Excluding Hypophosphatemia

OCCURRENCE	NEW GRADE 2	GRADE 3/4
1 st	Hold until $\leq$ Grade 1, then resume at same dose	Hold until $\leq$ Grade 1 or baseline, then reduce to 300 mg/day if at 400 mg dose level, or to 400 mg/day if at 600 mg dose level.
2 nd	Hold until $\leq$ Grade 1 then reduce to 300 mg/day if at 400 mg dose level, or to 400 mg/day if at 600 mg dose level.	Stop treatment
3 rd	Stop treatment	N/A

### 5.5 Dose Modifications For Hematological Toxicity

#### 5.5.1 Grade 1/2

No dose interruptions or reductions will be performed for Grade 1/2 hematological toxicity.

#### 5.5.2 Grade 3/4

If the patient experiences a Grade 3/4 hematological toxicity, defined as an ANC  $< 1 \times 10^9/L$ , or a platelet count  $< 50 \times 10^9/L$ , Gleevec must be withheld until the toxicity has resolved to  $\leq$  Grade 2. ANC will take precedence over a WBC count in determining the degree of neutropenia (e.g., doses should not be interrupted for a patient with a WBC  $< 2.0 \times 10^9 /L$ , but would be for an ANC  $< 1 \times 10^9/L$ ). If the toxicity resolves to  $\leq$  Grade 2 within 2 weeks, Gleevec treatment may be resumed at the same dose. If the Grade 3/4 toxicity recurs, Gleevec must be withheld. If the toxicity resolves to  $\leq$  Grade 2 within 2 weeks, Gleevec may be recommenced with the daily dose reduced by 100 mg if at 400 mg dose level, or by 200 mg if at 600 mg dose level. If the Grade 3/4 toxicity persists for longer than 2 weeks, Gleevec will be stopped. If the Grade 3/4 toxicity recurs after a dose reduction to 300 mg/day, Gleevec treatment will be stopped. Patients may receive G-CSF while Gleevec is held as clinically indicated.

No dose reductions will be performed for Grade 1-4 anemia. If the patient develops anemia, he/she may be transfused or receive Erythropoietin at the discretion of the Investigator.

## Summary of Dose Modifications for Hematologic Toxicity

OCCURRENCE	GRADE 3/4
1 st	Hold until $\leq$ Grade 2 within 2 weeks, then resume at same dose. If $\leq$ Grade 2 not reached within 2 weeks, then stop treatment.
2 nd -Dose >300 mg	Hold until $\leq$ Grade 2 within 2 weeks, then resume treatment at 300 mg/day if at 400 mg dose level, or by 200 mg if at 600 mg dose level. If $\leq$ Grade 2 not reached in 2 weeks, then stop treatment.
2 nd – Dose = 300 mg Dose at 2 nd occurrence	Stop treatment.

### 5.6 Concomitant Therapy

In general, concomitant medications and therapies deemed necessary for the supportive care and safety of the patient are allowed, provided their use is documented in the patient records and on the appropriate CRF. The administration of any other therapies intended to treat the primary condition, including chemotherapy and biologic agents, is NOT permitted. Similarly, the use of other concurrent investigational drugs is not allowed.

Because of the inherent risk of either reduced activity or enhanced toxicity of the concomitant medication and/or Gleevec, drugs known to interact with the same CYP450 isoenzymes (2D6 and 3A4) as Gleevec should be used with caution. Patients using concomitant medications known to be metabolized by these cytochrome p450 enzymes will not be excluded from the study. However, the patients must be carefully monitored for potentiation of toxicity due to individual concomitant medication. Special care has to be given to the concomitant use of acetaminophen (e.g., Tylenol® or Percocet®, paracetamol Panadol®, etc.) with Gleevec. Any use of concomitant medication must be captured in the concomitant medication CRF. (See Appendix XV for complete list).

## 5.7 Permitted Medications

- 5.7.1 Prophylactic use of loperamide (e.g., Imodium®, with suggested dosing as start: 4mg po x 1, then 2 mg po after each loose stool, max 16 mg/day) is recommended for patients experiencing Grade 1 or 2 diarrhea, before dose interruption.
- 5.7.2 Chemoprophylaxis for *Pneumocystis carinii* pneumonia is highly recommended for all subjects with a CD4 count of  $\leq 200$ .
- 5.7.3 Topical and/or oral antifungal agents are permitted except oral itraconazole and ketoconazole. (Topical agents should not be applied to study lesions).
- 5.7.4 Chemoprophylaxis for *Mycobacterium avium* complex (MAC) is required for patients whose CD4 cell counts  $< 50$  cells/mm^3, preferably with azithromycin 1.2 g orally once a week.
- 5.7.5 Treatment, maintenance or chemoprophylaxis with approved agents for OI as clinically indicated.
- 5.7.6 All antibiotics as clinically indicated except for prohibited medications.
- 5.7.7 Antiretroviral therapy is permitted and strongly encouraged for any subject with a detectable viral load. Patient should be receiving an optimal and stable regimen of HAART for a minimum of 12 weeks prior to entry.
- 5.7.8 Erythropoietin is permitted at the discretion of the Investigator.
- 5.7.9 Granulocyte colony stimulating factors are permitted as outlined in Sections 3.2.12 and 5.6.
- 5.7.10 Regularly prescribed medications such as antipyretics, analgesics, allergy medications, antidepressants, sleep medications, oral contraceptives, megestrol acetate, testosterone or any other medications are permitted except for prohibited medications (see Section 5.8.1.4 – 5.8.1.7).
- 5.7.11 Prophylactic anti-emetics should be withheld until the patient has experienced Grade 1 nausea or vomiting.
- 5.7.12 If patient has weight gain greater than 5 pounds above baseline that is felt to be due to fluid retention, patient may be started on diuretics at the Investigator's discretion.

- 5.7.13 Alternative therapies such as vitamins, acupuncture and visualization techniques will be permitted. Subjects should report the use of these therapies and they will be recorded.

## **5.8 Prohibited Medications**

- 5.8.1 Investigational drugs, with the exception of antiretroviral agents that are being obtained through an expanded access protocol.
- 5.8.2 Systemic cytotoxic chemotherapy or any other treatment specifically prescribed to treat KS (e.g., radiation, etc.).
- 5.8.3 Since warfarin is metabolized through the CYP450 system, no therapeutic anticoagulation with warfarin (e.g. Coumadin) will be permitted in patients participating in this study. As an alternative, therapeutic anticoagulation may be accomplished using low-molecular weight heparin (e.g., Lovenox®) or heparin. A mini-dose coumadin derivative (equivalent to 1 mg QD Coumadin) is permitted for prophylaxis of central venous catheter thrombosis, at the discretion of the treating physician. In general, the use of Coumadin is discouraged on this protocol.
- 5.8.4 The routine use of systemic corticosteroid therapy, other than replacement doses, is not permitted.

## **5.9 Prohibited Foods**

- 5.9.1 Grapefruit juice.

## **5.10 Treatment Compliance**

Records of study medication used, dosages administered, and intervals between visits will be kept during the study. Drug accountability will be noted and at the completion of the trial. Patients will be asked to return all unused medication at the monthly visits.

Patients will also be given a diary to carry home and will be instructed to record each time study drug is administered. The patient will be asked to bring diary at each clinic visit.

Patients will be asked to weigh themselves twice a week and will be asked to report to the study team any increase in weight greater than 5 pounds above baseline. If weight gain is felt to be due to fluid retention, patient may be started on diuretics at the Investigator's discretion.

## 6.0 REPORTING OF ADVERSE EVENTS

This study will utilize the CTCAE version 3.0 for Common Terminology Criteria for Adverse Event reporting. A copy of the CTCAE version 3.0 can be downloaded from the CTEP home page (<http://ctep.info.nih.gov>). All appropriate treatment areas should have access to a copy of the CTCAE version 3.0. The documents “NCI Guidelines: Adverse Event Reporting Requirements for NCI Investigational Agents” (sections 2 and 3) clearly outline reporting criteria.

This study will be monitored by the Clinical Data Update System (CDUS). Cumulative CDUS data will be submitted quarterly to CTEP by electronic means. Reports are due January 31, April 30, July 31, and October 31.

